Hypothesis #1B: *Whole blood resuscitation will be associated with a lower incidence of 12 hour and 24 hour mortality, a lower incidence of death from exsanguination, incidence of MOF, nosocomial infection, improved transfusion ratios, lower overall blood transfusion requirements and shorter time to hemostasis as compared to those resuscitated with component therapy.*

Hypothesis #1C: *Whole blood resuscitation will be associated with an improved Glasgow Outcome Score-Extended at 6 months post injury as compared to those resuscitated with component therapy in patients with traumatic brain injury.*

Hypothesis #2A: *A nadir prehospital and acute phase resuscitation systolic blood pressure greater than or equal to 120 mmHg will be associated with improved traumatic brain injury outcomes at discharge and at 6 months.*

Linking Investigations in Trauma and Emergency Services

Task Order 2: Shock, Whole blood and Assessment of TBI (SWAT)

Hypothesis #2B: *The magnitude of the dose depth curve of systolic blood pressure during the prehospital and acute phase resuscitation will be associated with neurological outcome differences at discharge and at 6 months following traumatic brain injury.*

Research Design and Methods

Study Design: The LITES Network will perform a multicenter, prospective, observational cohort study over a 4 year period to determine the impact of whole blood resuscitation in trauma patients with hemorrhagic shock at risk of large volume resuscitation with and without TBI. Early whole blood resuscitation will be compared to standard component resuscitation. The study will also further characterize blood pressure and resuscitation endpoints in poly-trauma patients with traumatic brain injury. Six trauma sites with appropriate characteristics will be selected from network sites across the country. (Figure 2)

Figure 2

Study Setting: The study will be performed utilizing busy level I trauma centers from within the LITES Network located across the country, at sites where either whole blood has currently been incorporated into standard of care or where component blood transfusion is being utilized for patients in hemorrhagic shock at risk for large volume resuscitation. Due to the paucity of trauma centers who are currently utilizing whole blood for trauma patients as standard of care, the potential to incorporate additional sites may be required over time.

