Sample Tracking, Management and Storage: After sample obtainment, processing and storage, samples will initially be batched sent to the University of Pittsburgh biological sample repository where it will be tracked, managed and stored until the necessary translational or mechanistic measurement are performed. The CCC and DCC have a long track record of coordinating such processes.

Power Analysis: The prospective cohort study will utilize time to 4 hour mortality for its primary outcome to power the study. Based upon the 6 LITES Network sites admission history that will be utilized and their respective volume of hemorrhagic shock patients meeting inclusion and exclusion criteria and a 3.5 year enrollment time period, we plan to initiate sampling on 1,050 patients over the enrollment time period of the study. With an 85% consent rate which is an estimate based upon prior studies of similar nature, we will consent for participation 892 patients for the study. With an estimate baseline rate of 4 hour mortality of 11.1 % derived from the PROPPR study, there will be 90% power to detect a hazard ratio of 1.9.

Calculations are based on the primary aim of the study based on the following assumptions:

- Type I error rate of 0.05
- Two-sided alternative hypothesis

Linking Investigations in Trauma and Emergency Services

Task Order 2: Shock, Whole blood and Assessment of TBI (SWAT)

- 6 sites will be involved, three whole blood and three component sites
- Each site will enroll 175 participants in 3.5 years of enrollment, of which, 85% will be eligible for the study (149)
- The calculations are based on Cox proportional hazard model
- A 4 hour event rate in the control (non-whole blood) group of 0.111

The power calculations for these secondary aims are presented below. When reporting the results of the analyses, caution will need to be taken with respect to the interpretation of the findings since they are secondary in nature.

The secondary outcomes in Aim 1B include binary outcome, continuous outcomes, and time to event outcomes. For the binary outcomes, the odds ratio that can be detected is presented in Table 1. For the continuous outcome, the effect size that can be detected is 0.13. Finally, for the time to event outcomes, the hazard ratio that can be detected over a range of event rates in the control group is also presented in Table 1.

Event Rate	.1	.2	.3	.4	.5	.6
Odds Ratio	1.76	1.56	1.49	1.46	1.46	1.48
Hazard Rate	2.69	1.70	.37	.30	.27	.30

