- For Aim 1C, a nonparametric analysis of variance will be used to compare the distribution of the GOS-E between the two groups. An effect size of 0.17 could be detected.
- For aim 2A, a nonparametric analysis of variance will be used to compare the distribution of the GOS-E between the two groups. An effect size of 0.28 could be detected.
- For aim 2B, a nonparametric correlation coefficient will be used to assess the association between GOS-E and the area under the systolic blood pressure curve. For each, a 95% confidence interval with a width of 0.19 can be estimated.
- For all secondary analyses, the type I error rate was set to 0.05, with a two-sided alternative hypothesis, and 90% power. For the Aim 1, the sample size will be 1,190. For Aim 2, the sample size will be limited to those with a traumatic brain injury. For the purposes of this study, this is expected to be 35% or a total of 417 participants.

Analyses

AIM#1: The analysis will begin by describing the baseline demographic and clinical characteristics of the overall population and then stratified by whole blood usage. The characteristics will be

Linking Investigations in Trauma and Emergency Services

Task Order 2: Shock, Whole blood and Assessment of TBI (SWAT)

compared among those who receive and who do not receive whole blood. For discrete variables, proportions will be generated and a chi-square test will be used to test for differences between the proportions. For continuous characteristics, means (medians) and standard deviations (interquartile ranges) will be calculated and t-tests (Wilcoxon) will be used to compare the means (distributions) among those who receive and do not receive whole blood.

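### The secondary power figures assume 1,190 patients (417 with TBI), but the six-site design yields 1,050 sampled and 892 consented (about 312 with TBI), so the sample size or the stated power is wrong.

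*Combined protocol and SAP*

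**What the plan says.** All of this is in the combined protocol and SAP.

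- **Number of sites.** Study Design: "Six trauma sites with appropriate characteristics will be selected from network sites across the country". Power Analysis assumptions: "6 sites will be involved, three whole blood and three component sites".
- **Planned numbers.** Power Analysis: "we plan to initiate sampling on 1,050 patients over the enrollment time period of the study", and after consent "we will consent for participation 892 patients for the study".
- **The 85% factor.** The main text of Power Analysis describes it this way: "With an 85% consent rate which is an estimate based upon prior studies of similar nature". The assumption list describes it differently: "Each site will enroll 175 participants in 3.5 years of enrollment, of which, 85% will be eligible for the study (149". So it is a consent rate in one place and an eligibility rate in the other.
- **Secondary aims.** The end of Power Analysis sets two-sided 0.05 and 90% power for all secondary analyses, and then: "For the Aim 1, the sample size will be 1,190". Aim 2 is limited to TBI patients, taken as 35%, or 417.
- **Printed secondary figures.** Detectable odds ratios are 1.76, 1.56, 1.49, 1.46, 1.46 and 1.48 at event rates 0.1 to 0.6. Effect sizes are 0.13 (continuous outcomes), 0.17 (Aim 1C) and 0.28 (Aim 2A). The Aim 2B 95% interval width is 0.19.
- **Possible growth.** Study Setting notes that "the potential to incorporate additional sites may be required over time". Whole Blood Transfusion Sites also foresees further sites. Neither gives a number.

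**The concern.** The figure of 1,190 is larger than the number from whom sampling will even begin. No consent or eligibility assumption applied to six sites of 175 can produce it. If the secondary figures were computed at 1,190 and 417, they describe a larger study than the one planned.

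Readers will use these figures to judge what a null secondary result can exclude. That matters most for six-month GOS-E, which the plan makes the principal outcome of its principal subgroup. There the assumed number is about a third too large (417/312 = 1.34), before any loss to follow-up.

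**Working it through.** **1. Sample sizes.** The inputs are those of Power Analysis.
- Sampled: 6 × 175 = 1,050. Consented: 0.85 × 1,050 = 892.5, stated as 892.
- TBI at 35%: 0.35 × 1,190 = 416.5 (the plan's 417); 0.35 × 892 = 312; 0.35 × 1,050 = 367.5.
- For comparison, 8 × 175 × 0.85 = 1,190 exactly.

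**2. Odds ratios.** The method is two independent proportions with pooled variance under the null, two-sided 0.05, equal groups and no clustering. With p2 = p1·OR/(1 − p1 + p1·OR), power = Φ[(|p2 − p1| − 1.96·SE0)/SE1].

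Example at p1 = 0.1 and OR 1.76: p2 = 0.176/1.076 = 0.1636.
- 595 per group: SE0 = 0.01961, SE1 = 0.01952, power = Φ[(0.0636 − 0.0384)/0.01952] = 0.90.
- 446 per group: SE0 = 0.02265, SE1 = 0.02255, power = Φ[(0.0636 − 0.0444)/0.02255] = 0.80.

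| Total N, power | 0.1 | 0.2 | 0.3 | 0.4 | 0.5 | 0.6 |
|---|---|---|---|---|---|---|
| Printed | 1.76 | 1.56 | 1.49 | 1.46 | 1.46 | 1.48 |
| 1,190, 90% | 1.758 | 1.557 | 1.487 | 1.460 | 1.459 | 1.482 |
| 1,050, 90% | 1.82 | 1.60 | 1.52 | 1.50 | 1.50 | 1.52 |
| 892, 90% | 1.90 | 1.66 | 1.58 | 1.55 | 1.55 | 1.58 |
| 892, 80% | 1.757 | 1.556 | 1.486 | 1.459 | 1.459 | 1.482 |

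The plan's row is reproduced at 1,190 and 90%. Power at the printed values is 85.8% to 86.5% with 1,050 and 79.8% to 80.6% with 892. The row also appears at 892 and 80%. This is because the sample-size constants are in the ratio (2.8016/3.2415)² = 0.747, and 892/1,190 = 0.750.

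Whole Blood Transfusion Sites plans for 33% of patients at whole blood sites. With one third on whole blood, power at the printed values is 81% to 83% with 1,050 and 75% to 77% with 892.

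**3. Aim 2B width.** The Fisher z interval at r = 0 has width 2·tanh(1.96/√(n − 3)).
- n = 417: 0.192, the printed 0.19.
- n = 367: 0.205.
- n = 312: 0.222.

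At n = 312 the width is 0.202 at r = 0.3 and 0.187 at r = 0.4. It reaches 0.19 only when r is about 0.4.

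**4. Effect sizes.** The plan names no metric, so each match below is an inference.
- **0.13 (continuous outcomes).** A paired calculation with 1,190/2 = 595 pairs at 90% power gives 3.2415/√595 = 0.133. The Hypothesis#1B analysis does name a t-test for correlated means, but the patients are not paired. For independent groups, 3.2415 × √(4/N) gives 0.19 at 1,190, 0.20 at 1,050 and 0.22 at 892.
- **0.17 (Aim 1C).** A standardised difference with Wilcoxon efficiency 0.955 at 80% power gives 2.8016 × √(4/1,190)/√0.955 = 0.166.
- **0.28 (Aim 2A).** The same formula at 417 gives 0.281.

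So 0.13 fits 90% power, while 0.17 and 0.28 fit 80%. If these matches are right, Aim 1C was computed on the whole cohort, although Hypothesis #1C concerns TBI patients. At 312 patients, 90% power and an even split, the detectable standardised difference is 3.2415 × √(4/312) = 0.37, or 0.38 after dividing by √0.955.

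The hazard row of the same table is not used here, because its values may not be legible in the text available.

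**The case against.** **The printed row may be right and only the power label wrong.** At 892 and 80% power all six odds ratios are correct, so a flat claim that they fall short of their power is not supported. What stands is that the plan states 90% and 1,190, and the six-site design cannot deliver both. The Aim 2B width does not depend on power. It fits 417 near zero correlation, but a true correlation of about 0.4 would bring it to 0.19 even at 312.

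**More sites may join.** The plan foresees this in two places. It gives no number, and Power Analysis is fixed at six. A reader might infer an eight-site version from 8 × 175 × 0.85 = 1,190. The documents do not mention one.

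**Data collected under the waiver are kept without consent.** Recruitment and Consent says so for the first 36 hours. If the 85% is a consent rate, outcomes complete in that window can use up to 1,050, which gives about 86% power. Seven-day organ failure, 30-day infection and six-month GOS-E cannot. If the 85% is an eligibility rate, 892 applies throughout.

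**Other readings of the effect sizes.** A reader might take 0.17 as Cohen's f in TBI patients (0.171 at 417 with rank efficiency 0.864) and conclude that Aim 1C already rests on them. That reading leaves 0.28 unexplained, and the text does not say it.

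**The primary figure.** A reader might infer that the primary hazard ratio of 1.9 also rests on 1,190. With equal groups and 90% power, the detectable ratio at 892 is 1.76 if whole blood has the higher hazard and 2.13 (as a reciprocal) if lower; at 1,190 these are 1.64 and 1.90. The last value is suggestive, but the plan ties its 1.9 to the 892-patient design, gives no direction for it, and uses 1,190 only for secondary aims. That inference is not part of this point.

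**The consequence is modest.** The plan already urges caution with secondary findings. That caution does not correct a sample size.

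**Conclusion.** The point holds as an internal contradiction. The secondary figures use 1,190 and 417, while the stated six-site design gives 1,050 sampled, 892 consented and about 312 with TBI (at most about 367).

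- **Odds ratios.** Taking the stated 90% as intended, the detectable values rise by 0.03 to 0.06 at 1,050 and by 0.09 to 0.14 at 892. If 80% was intended, they are right for 892 and the power statement is wrong.
- **Aim 2B.** The width near zero correlation is about 0.22, not 0.19.
- **Effect sizes.** They appear to mix a paired calculation at 90% power with unpaired rank calculations at 80%. Because this is inferred, no power shortfall is claimed for them.

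The odds-ratio figures assume equal groups unless stated otherwise and no site clustering. The aims are secondary, and the primary analysis is unaffected. It is worth correcting, but it does not threaten the study's main conclusion.

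**What to change.** 1. Settle whether the 85% is a consent or an eligibility rate. Then restate the secondary sample size from the design: 892 for outcomes that need consent, up to 1,050 for outcomes complete within the 36-hour waiver (only if the 85% is a consent rate), and about 312 for TBI analyses. If 1,190 is intended, state the sites that support it and align the rest of Power Analysis.
2. Recompute every dependent figure at that sample size, with one stated power and one allocation (three and three sites, or 33% whole blood).
3. Name the effect-size metric and use an independent-groups formula.
4. Recompute Aim 1C in TBI patients: about 0.37 to 0.38 as a standardised difference at 312, 90% power and an even split.
5. State that the Aim 2B width is for a correlation near zero.

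The cost is one rewritten paragraph and one table, with no change to enrolment. The downside is less favourable stated figures for the secondary aims.

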Primary Study Outcome: The cohort study will be principally powered using 4 hour mortality as the primary outcome. This outcome was found to be significantly different across treatment arms in the recent PROPPR trial and early mortality time points have recently been recommended and deemed most appropriate for hemorrhagic shock clinical trials.^{24,43} Promoting survival beyond this time period may represent the critical period that is required for an injured patient to be transported to a higher echelon of care, particularly when injury occurs in austere environments.

Secondary Non-TBI Clinical Outcomes: Secondary clinical outcomes will include 12 hr mortality, 24hr mortality, 28 day mortality, time to hemostasis (defined by a WB or PRBC transfusion rate; ≤ 1 unit/hour and surgeon directed intraoperative assessment), death from exsanguination/hemorrhage, blood and blood component transfusion requirements (over 1st four hours and total at 24hrs), Multiple Organ Failure, nosocomial infection, transfusion reaction, venous thromboembolism (VTE), ICU free days and ventilator free days.

TBI Specific Outcomes: For the overall TBI subgroup, the principle outcome will be 6 month Extended Glasgow Outcome Scale (GOS-E). Additional TBI specific outcomes will include hemodynamic parameters (serial systolic and diastolic blood pressure and heart rate measurements), prehospital, arrival, serial and discharge Glasgow Coma Scale scores, need for craniectomy/craniotomy, need for mannitol administration, need for paralysis, need for barbiturate coma, need for hypertonic saline administration, need for ICP monitoring, ICP pressures (initial, max daily x 7 days), TBI progression based upon serial CT imaging in initial 48 hours and Galveston Orientation and Amnesia Test (GOAT score) at discharge. Each accrual site will transfer the TBI patient's name, contact information, and basic injury characteristics, GOAT results, and discharge disposition to the Clinical Coordinating Center in Pittsburgh.

Linking Investigations in Trauma and Emergency Services

Task Order 2: Shock, Whole blood and Assessment of TBI (SWAT)

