Death from Exsanguination/Hemorrhage: Those patients who succumb on the operating table, IR suite or ICU due to uncontrolled coagulopathy or hemorrhage in the first 4 hours from arrival will have their mortality classified as exsanguination/hemorrhage. This will be determined by the individual trauma surgeon at the time of the event.

Acute Hemolytic Transfusion Reaction: We will utilize and characterize acute hemolytic transfusion reactions as defined by the CDC/National Healthcare Safety Network (NHSN) Hemovigilance Surveillance definition (www.cdc.gov/nhsn).

Linking Investigations in Trauma and Emergency Services

Task Order 2: Shock, Whole blood and Assessment of TBI (SWAT)

Galveston Orientation and Amnesia Test (GOAT): For TBI subjects, we will obtain the GOAT score at the time of discharge and the calculated score per standard methods.⁴⁸ (Figure 4) GOAT is a 10-item questionnaire used to quickly assess post-traumatic amnesia following head injury. The GOAT is read orally to the patient and may be easily administered at the bedside. The total score accounts for orientation of person, place, and time, and recollection of events pre and post-injury. Cutoff scores are available to identify abnormal, borderline, and normal orientation and it will additionally determine if a subject is able to provide continuing participation consent if consented by proxy.

Extended Glasgow Outcome Scale (6 months-GOSE): For TBI subjects, the GOSE score will be obtained at 6 months +/- 1month by hone survey or direct patient contact, whichever is feasible. For those TBI subjects who were unable to consent at discharge, the GOAT will be administered to assess their ability to provide direct consent, prior to the administration of the GOSE. When the assessment is done by phone, the verbal consent of participants who have regained the ability to consent, will be obtained to allow the GOSE to be completed. The score is able to characterize 6 month functional status into 8 well defined categories as shown in (Figure 5).

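### The detectable effect of 0.17 for Hypothesis 1C rests on the whole cohort of 1,190, but only TBI patients can contribute to 1C; in 417 TBI patients 0.17 has about 40% power

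*Combined protocol and SAP*

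**What the plan says.** Under Objectives/Specific Aims/Hypothesis, Hypothesis 1C predicts an "improved Glasgow Outcome Score-Extended at 6 months post injury as compared to those resuscitated with component therapy in patients with traumatic brain injury". The outcome definition for the extended Glasgow scale matches this: "For TBI subjects, the GOSE score will be obtained at 6 months". Table 1 marks the 6-month assessment as one for TBI subjects, and the outcomes section makes 6-month GOS-E the principal outcome of the TBI subgroup. No 6-month GOS-E is planned for patients without TBI.

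In the Power Analysis, the bullets for Aims 1C and 2A name the same method in the same words: "a nonparametric analysis of variance will be used to compare the distribution of the GOS-E between the two groups". For 1C the result is "An effect size of 0.17 could be detected"; for 2A it is "An effect size of 0.28 could be detected". The last bullet sets two-sided 0.05 and 90% power for all secondary analyses and then gives the sample sizes: "For the Aim 1, the sample size will be 1,190". Only Aim 2 is limited to TBI patients, expected to be 35% or 417. The same section elsewhere plans to sample 1,050 patients and consent 892.

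**The concern.** The sample size attached to 1C includes patients who will have no outcome for it. Aims 1C and 2A share the test, outcome, eligible patients, alpha and power, yet their detectable effects differ by a factor of about 1.65. That is roughly the factor expected if one was computed on 1,190 and the other on 417.

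Hypothesis 1C is the study's test of whole blood on the principal TBI outcome. If 0.17 is a whole-cohort value, the plan claims a sensitivity in TBI patients that it does not have, and anyone using the power section to interpret a null 1C result would start from the wrong figure.

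**Working it through.** **Inputs from the plan.** Aim 1 total 1,190; TBI share 35%, so 0.35 × 1,190 = 416.5, printed as 417; consented total 892, so 0.35 × 892 = 312; two-sided 0.05; 90% power; three whole-blood and three component sites with equal enrolment, i.e. an even split. The section on whole blood sites instead speaks of 33% of patients, which is used below as an alternative.

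**Assumptions not in the plan.** Effect size is read as a standardised difference *d*, and the rank test is given efficiency 3/π = 0.955 relative to the t-test. Clustering by site and missing GOS-E are ignored.

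**Formulas.** With *p* the whole-blood share and k = √(0.955 · N · p(1−p)):
- detectable d = (1.960 + z_power) / k, with z = 1.282 for 90% and 0.842 for 80%
- power at 0.17 = Φ(0.17k − 1.960)

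**1. Reproducing the plan's figures.** At N = 1,190, k = √(0.955 × 1,190 × 0.25) = 16.86.
- 90% power: 3.242/16.86 = 0.192, not 0.17 (0.188 without the rank correction).
- 80% power: 2.802/16.86 = 0.166, which rounds to 0.17.

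At N = 417, k = 9.98.
- 80% power: 2.802/9.98 = 0.281, which rounds to 0.28.
- 90% power: 3.242/9.98 = 0.325.

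So one convention (two-sided, 80%, rank test, even split) returns both printed values, with 1,190 behind 0.17 and 417 behind 0.28. It is not the stated 90%.

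**2. The ratio, which does not depend on the power level.** 0.28/0.17 = 1.65. Allowing for rounding, the range is 0.275/0.175 = 1.57 to 0.285/0.165 = 1.73. √(1,190/417) = 1.69 lies inside it.

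**3. Neighbouring figures.** The Aim 1B odds ratios all reproduce at close to 90% power with 595 per arm (for example, 0.901 at event rate 0.1 and odds ratio 1.76). The Aim 2B interval width of 0.19 reproduces at 417: 2 × 1.96/√414 = 0.193. The section does use 1,190 for Aim 1 and 417 for Aim 2.

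**4. Power of 0.17 where GOS-E exists (even split).**

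| N | k | 0.17k − 1.960 | Power |
|---|---|---|---|
| 1,190 | 16.86 | 0.905 | 82% |
| 417 | 9.98 | −0.264 | 40% |
| 312 | 8.63 | −0.493 | 31% |

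Without the rank correction these are 83%, 41% and 32%.

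**5. Detectable *d* at the stated 90%, rank test.**

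| TBI patients | Even split | 33% whole blood |
|---|---|---|
| 417 | 0.325 | 0.345 |
| 312 | 0.376 | 0.399 |

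With 417 patients and no rank correction, the even split gives 0.317. No other allocation gives less, so 0.17 cannot be a 90%-power standardised difference in the TBI subgroup.

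**The case against.** The strongest reply concerns the metric. The named test is an analysis of variance, whose usual effect size is Cohen's f, equal to d/2 for two equal groups. Read that way, the 90%-power value at 417 is 3.242/√417 = 0.159, or 0.162 with efficiency 0.955. With the lower-bound rank efficiency of 0.864 it is 0.171, so 0.17 could be a TBI figure at the stated power.

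This reading fails on Aim 2A. There, f = 0.28 in 417 patients would have over 99.9% power, not 90%. Uneven blood-pressure groups are likely in a shock cohort, and taking 0.28 as half a standardised difference of 0.56 would restore 90% with a split of about 10:90. The plan gives no such split. Moreover, f defined with group weights is d√(p(1−p)), and its detectable value depends only on the total N, so imbalance would not move it. Nor does the f reading remove the sentence assigning 1,190 to Aim 1. What stands is that the metric is undefined, so the power figures here are conditional on reading it as a standardised difference.

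A second reply is that the 0.13 for continuous Aim 1B outcomes does not fit the same formula at 1,190. It does fit a paired form with 595 pairs (3.242/√595 = 0.133), in line with the correlated-means t-test in the Analyses section. That again uses 1,190, but it shows that the section mixes conventions, so back-solving N from one printed figure alone would be weak evidence. The case rests on the explicit 1,190 together with the 1C/2A ratio.

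Finally, 1C is secondary, and the plan asks for caution with secondary findings. That limits the consequences but does not correct the number.

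**Conclusion.** The point holds. The text gives 1C a sample size of 1,190 although only TBI patients have the outcome, and the figures agree with that text. In the plan's own TBI population of 417, 0.17 has about 40% power, and about 31% if the TBI count is 312. These values assume a standardised difference, two-sided 0.05, an even split and a rank test. A 33% whole-blood share lowers them to about 36% and 28%, and site clustering or missing GOS-E would reduce sensitivity further.

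A reader might infer that the wrong population takes power from 90% to 40%. The documents do not support that: on the same assumptions 0.17 has only about 82% power at 1,190. The population error accounts for the fall from about 82% to 40%, and the gap between 90% and 82% is a separate discrepancy in the stated power. A reader might also infer that the study as a whole is underpowered, or that a null 1C result would be reported as excluding an effect. Neither follows: the study is powered on 4-hour mortality, and the plan states no such interpretation for 1C.

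**What to change.** - State in the Power Analysis that the population for Hypothesis 1C is the TBI subgroup, and remove 1C from the sentence assigning 1,190 to Aim 1.
- Define the effect-size metric and the assumed split between groups for 1C and 2A.
- Reconcile the totals of 1,190, 1,050 and 892, and base the TBI count on the result.
- Replace 0.17 with the value at the stated 90% power for that count. On the assumptions above this is about 0.33 with 417 or 0.38 with 312, or about 0.35 and 0.40 if 33% of patients receive whole blood.
- Check the 2A figure in the same pass: 0.28 at 417 with an even split corresponds to about 80% power, not 90%.

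The cost is a few sentences and a short recalculation. No patients, procedures or analyses change; the stated 1C figure becomes less favourable.
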